6.11. Training and GCP requirements for recruiting sites

Training in the trial procedures

Each clinician who will be involved in the trial at participating primary care sites (GP practices, CEDs, WICs and OOHs) will receive training in all trial recruitment and baseline data collection procedures prior to the start of recruitment. This will include how to train parents in administering the ear drops (for parents of children allocated to one of the two treatment arms) and completing the Symptom and Recovery Questionnaire, and will be provided by trial centre teams. A clinician training log will be maintained at sites and within the Trial Master File.

Clinicians at all participating primary care sites will also be offered ongoing support, recruitment advice and refresher training on request, by the study team.

GCP training requirements

In order to meet the requirements of ICH-GCP, of the MHRA (see: http://forums.mhra.gov.uk/showthread.php?33-MHRA-produced-FAQs-for-Investigator-Sites) and of the Medicines for Human Use (Clinical Trials) Regulations (Statutory Instrument 2004/1031 Schedule I, part 2 [7]) that "The medical care given to, and medical decisions made on behalf of, subjects shall always be the responsibility of an appropriately qualified doctor", specific arrangements will be put in place regarding the assessment of children's eligibility, the taking of informed consent and the administration of the trial IMP at recruiting sites.

These arrangements include provision for CEDAR eligibility assessments and IMP prescriptions to be made by appropriately trained (including GCP) non-medically qualified healthcare professionals, such as Advanced Nurse Practitioners/Prescribers (ANP), on the following grounds.

Risk of trial standards falling below those of standard clinical practice:

We have assessed the risks of ANP eligibility assessment and IMP prescription by ANPs to be consistent with the quality standards of the CEDAR trial, in line with the statements below:

- 1) The CEDAR eligibility criteria do not require the interpretation of diagnostic tests
- 2) The CEDAR recruitment processes are consistent with the responsibilities of a suitably qualified ANP within standard clinical practice
- 3) The diagnosis and routine management of AOM by a suitably qualified ANP is consistent with standard clinical practice
- 4) The prescribing of a topical analgesic by a suitably qualified ANP is consistent with standard clinical practice
- 5) All ANPs participating in the trial will be appropriately qualified and will be assessing and managing children with AOM as part of their routine responsibilities
- 6) All ANPs participating in the trial will have GCP training and will receive face-to-face training by the study team
- 7) All site staff roles and responsibilities will be documented on the delegation log which will be authorised by a medically qualified, GCP trained doctor.

Availability of GCP-trained GP or other medically qualified doctor:

- 8) For sites at which a GCP-trained GP or other medically qualified doctor is present, the site training and delegation logs will be authorised by this GP/doctor.
- 9) For Nurse-led sites at which a GCP-trained GP or other medically qualified doctor is not normally present, the site training and delegation logs will be authorised by the local CEDAR trial centre PI, acting as the GCP-trained GP.
- 10) Recruitment by ANPs at sites at which a GCP-trained GP or other medically qualified doctor is present will be overseen by this GCP-trained GP or other medically qualified doctor, and this oversight will take the form of GP/doctor authorisation of the completed trial prescriptions within a reasonable timescale following recruitment.
- 11) Recruitment from Nurse-led sites at which a GCP-trained GP or other medically qualified doctor is not normally present will be overseen by the CEDAR Chief Investigator as the medically qualified doctor. This oversight will take the form of authorisation of the completed trial prescriptions by the CEDAR CI (or another delegated GCP-trained GP, if the CI is not available) within a reasonable timescale following recruitment.
- 12) In all situations where a GCP-trained GP or medically qualified doctor is not available at a ANP recruitment site, if the ANP needs exceptional medical advice regarding a borderline eligility decision, the ANP will be able to contact a GCP-trained GP via the trial team through an auditable process which will be described in a SOP.

(i) Eligibility assessment

The eligibility of children to take part in CEDAR must be assessed by:

(a) a GCP-trained GP or other medically qualified doctor who has been trained in the trial procedures, OR;

- (b) a suitably qualified and GCP-trained Nurse or other healthcare professional, who has been trained in the trial procedures, and with oversight from a GCP-trained GP or other medically qualified doctor (oversight in this instance is confirmation that the eligibility decision is correct, established by means of the GCP-trained doctor's signature on the trial prescription prior to the issue of the trial medication), OR
- (c) A suitably qualified and GCP-trained Advanced Nurse Prescriber/Practitioner who has been trained in the trial procedures, with oversight from a GCP-trained GP or other medically qualified doctor (oversight in this instance is confirmation that the eligibility decision is correct, established by means of the GCP-trained doctor's signature on the trial prescription within a reasonable time scale following recruitment, as above).

(ii) Consent

Informed consent (which may or may not be accompanied by child assent, depending on the age and understanding of the child and at the discretion of the clinician and parent) will be obtained for all children by:

- (d) a GCP-trained GP or Nurse who has been trained in the trial procedures, OR;
- (e) a non GCP-trained healthcare professional (GP or Nurse) who has been trained in the trial procedures by a GCP-trained GP, and with oversight from a GCP-trained GP (oversight in this instance is: (1) written confirmation from a GCP-trained GP that the member of staff is sufficiently qualified and experienced to take consent, on behalf of the recruiting site, for this trial; and (2) countersignature on the consent form by the GCP-trained GP prior to the issue of the trial medication).

(iii) Issue of the trial medication

The trial medication may be issued to the parents of participating children, who have been recruited to one of the two ear drop arms, by a suitably qualified and GCP-trained GP, Nurse or other healthcare professional who has received training in the trial procedures.

Persons authorised to undertake the above activities on behalf of the recruiting site, will be documented on the trial delegation log.

Evidence of GCP training or renewal of initial GCP training, in line with local CCG practice (for Wales, we will refer to the normal practice of the Local Health Board via NISCHR), and within the last five years, will be requested and stored in the Trial Master File. The study team will provide support to recruiting sites in identifying locally available GCP training and in liaising with local CRN staff to ensure that this is made available to participating clinicians.

7. TRIAL MEDICINES

7.1. Investigational Medicinal Product and Comparator

The Investigational Medicinal Product (IMP) for this trial will be Auralgan©, manufactured by Pfizer Consumer Healthcare (Australia) and sold in 15mL bottles, or equivalent branded or bespoke manufactured product with the same constituents, against a matched placebo. Auralgan© is an oil based, combined local anaesthetic (benzocaine) and analgesic (phenazone, International Nonproprietary Name, also known in the US as antipyrine) otic solution (ear drop), sold in 15mL bottles and containing 14 mg/mL (1.4%) of benzocaine and 54mg/mL (5.4%) phenazone suspended in a glycerine-based liquid along with a preservative (hydroxyquinolone sulphate). The manufacturing authorisation for Auralgan is AUST R 10460 and this is held by Pfizer Consumer Healthcare (Australia). The supplier contracted for the trial (Albany Molecular Research Inc) will be responsible for the importation of the active IMP and for the manufacture of the placebo. Placebo solution will be manufactured to match the active solution for appearance, weight, texture and packaging, such that allocation concealment and blinding of the trial is maintained.

7.2. Packaging, labelling and dispensing

The supplier will be responsible for packaging the active and placebo medicines into identical containers and for labelling them under their MIA (IMP) license. The labelling of medication packs will be MHRA-approved and conform to Annexe 13 (GMP) and Article 13.3 of Directive 2001/20/EC. A template label will be provided by the supplier and approved by UH Bristol Pharmacy on behalf of the Sponsor in line with the Service Level Agreement (SLA), and by the Chief Investigator.

Each Medication Pack will have a Medicine ID number, randomly generated to ensure active and placebo ear drop solution bottles are indistinguishable (e.g. avoid all placebo bottles being assigned an odd number) and thus maintain allocation concealment. This random number will be generated by the Bristol Randomised Trials Collaboration and provided to the supplier who will use it to form the medicine identifier (Medicine ID Number) and include it with the open code break document sent with each delivery of trial Medicine Packs to UH Bristol Pharmacy. Each Medicine Pack will contain two bottles of either the active or the placebo solution.

The Medicine Packs will be received from the supplier and stored by the Pharmacy at University Hospitals Bristol NHS Foundation Trust (UH Bristol Pharmacy). A randomisation schedule will be provided to the supplier and to UH Bristol Pharmacy by the Bristol Randomised Trials Collaboration (BRTC) assigning active vs. placebo treatment to each Participant ID number (an interim 2-arm randomisation schedule will be applied for the 2 arm pilot at the start of the trial). The Participant ID number will have two digits will be configured to identify whether the child has been recruited into the RCT or OCS, the trial Centre in which they were recruited, followed by a sequence of digits.

All RCT Patient Packs will be pre-labelled with the Participant ID number and will contain: (i) either a medicine pack (containing either 2 bottles of active solution, or 2 bottles of placebo) or an ethically approved non-medicinal item of equivalent weight, in order to maintain clinician concealment up to the point of randomisation; (ii) relevant items of trial paperwork (including the Symptom and Recovery Questionnaire and Trial Participation Card) and equipment (including a trial pen, a small gift appropriate for participating children, and a trial tote bag), and (iii) an appropriate number of pre-printed Participant ID number labels to affix to the trial paperwork for subject identification purposes. All OCS Patient Packs, also pre-labelled with the Participant ID number, will contain items (ii) and (iii) only. The Bristol trial centre will make up the patient packs (minus the medicine packs) and provide them to UH Bristol Pharmacy. UH Bristol Pharmacy will add to the Patient Packs a Medicine Pack in line with the randomisation schedule provided by BRTC. UH Bristol Pharmacy will keep a log of which Medicine Pack is allocated to which Patient Pack and will affix the appropriate Medicine ID and Participant ID numbers to the Trial Participation Card. Complete, sealed Patient Packs will be stored by UH Bristol Pharmacy and released by a pharmacist to the Bristol trial centre in batches for direct onward distribution to recruiting primary care sites.

The Bristol trial centre will supply all participating primary care sites (including those led by Cardiff or Southampton) in small batches (of two RCT Patient Packs for the 2 arm pilot, increasing to batches of 3 once the placebo arm is introduced size to be confirmed), via same-day courier service in line with all applicable regulations. The Bristol trial centre will be the single point of contact for UH Bristol Pharmacy for the purposes of the trial. The Bristol trial centre will keep a log of which Patient Packs are sent to which recruiting primary care site, with all Patient Packs signed for on receipt at the GP practice and a faxed, completed requisition and transfer form will be sent to the Bristol trial Centre detailing the Participant ID numbers received at the site. Sites will liaise with their local Centre when more packs are required, and the local centre will then make a request for additional packs to the Bristol Centre, which will send a further batch directly to the recruiting primary care site.

From the point at which the placebo is available, participating sites will be transferred from the 2 arm pilot into the 3 arm trial once they have used up their allocation of 2 arm Patient Packs. Any new site joining the trial after the point of placebo availability will be set up to run the 3 arm trial.

Recruiting primary care sites will store the medicines in the manner approved by the MHRA and protect them from light and excessive humidity.

On completion of the baseline questionnaire (CRF) online the clinician will enter the Patient ID number.

7.3. Storage and transport

The product information supplied by the manufacturer (Pfizer Australia) indicates that the medicine should be stored under 25°C. We intend to store and transport the medicines in line with standard clinical shipping and storage practice in the country of manufacture and as approved by the MHRA for use in this trial. The supplier will be responsible for importing the active medicine and for ensuring that the product has not suffered any loss of quality on receipt in the UK.

The storage environment will be secure (i.e. a locked cabinet or room) with access limited to members of the practice team recorded as being involved in the trial.

A formal trial risk assessment will be undertaken for each location at which the trial medicines will be stored.

7.4. Dosing regimen

According to the randomisation schedule for the full trial, a child participating in the RCT will receive either active ear drops, placebo ear drops or no drops (children participating in the initial 2 arm pilot will receive either active ear drops or no ear drops). Children participating in the OCS will not receive any ear drops.

For children allocated to either of the two treatment arms within the RCT (active ear drops plus usual care, or placebo ear drops plus usual care), the allocation will be unknown to the clinician, parent, child and to the research team (with the exception of the Trial Pharmacist at UH Bristol Pharmacy). For children recruited during the 2 arm pilot, allocation to active ear drops will be known at the point of recruitment, following the assessment of eligibility and informed consent processes.

Regardless of allocation, parents in the two treatment arms will be asked to administer the ear drops no more than every 2 hours and a maximum of 12 times daily, in one or both ears to a maximum age-specific dosage per child, until pain is relieved, and for a maximum of 8 days. Missed doses should not be compensated for by giving a larger dose or more frequent doses. Clear dosage instructions will be provided on the medicine bottle and in the trial instructions for parents on how to give ear drops.

We anticipate that for 50% of children the duration of treatment until pain relieved will be 3 days, and that 90% of children's symptoms will have resolved by 8 days¹⁷.

There are no special dietary or other requirements to be imposed.

7.5. Drug accountability

A formal SOP will be developed to detail the processes and documentation associated with each step.

Activity	Responsibility
QP release of medicine packs labelled with Medicine Pack ID and	Supplier
Participant ID in line with randomisation schedule provided by BRTC	
Put together Patient Packs, minus the trial medicines but identified	Bristol Centre
by unique Participant ID numbers, and supply to UH Bristol Pharmacy	
Receive Medicine Packs (identified by unique Medicine ID numbers	UH Bristol Pharmacy
and Participant ID numbers, in line with BRTC randomisation	
schedule) from supplier	
Allocate Medicine Packs to Participant Packs as per randomisation	UH Bristol Pharmacy
schedule, and attach Medicine ID/Participant ID label to Trial	
Participation Card	

Activity	Responsibility
Send Patient Packs (numbered by Participant ID number, in batches,	UH Bristol Pharmacy
to Bristol trial centre via same-day courier service	
Receive Patient Packs from UH Bristol Pharmacy and store	Bristol Trial Centre
appropriately	
Send Patient Packs to sites via same-day or next-day (but not Friday-	Bristol Trial Centre
Monday) courier service	
Receive Patient Packs and associated medicines from Bristol trial	Sites
centre and store appropriately	
Prescribe and dispense medicines to the parent, and record the	Sites
dispensing information on the GP site drug accountability log	
Order more supplies	Sites from Bristol Centre. Bristol
	Centre from UH Bristol Pharmacy
Return of unused trial medicines	Parents will return unused medicine
	to Bristol centre in a stamped
	addressed envelope. Bristol centre
	will deliver to UH Bristol Pharmacy
Destruction of unused trial medicines	UH Bristol Pharmacy
Unblinding	UH Bristol Pharmacy

7.6. Subject compliance

Adherence to medication will be measured using a daily Symptom and Recovery Questionnaire similar to those used in our previous trials [6,7] and primary analyses conducted on an intention to treat basis.

Subject compliance will be measured in two ways:

- The parent will be asked, at each of the 8 time points within the Symptom and Recovery Questionnaire (post recruitment on Day 1; in the evening, i.e. 24-36 hours post recruitment on Day 2; every evening for Days 3-8), how many times they have administered the trial medicines to either ear of the child. The completion of the paper or online Symptom and Recovery Questionnaire will be supported by regular telephone calls from the study team (*frequency and time points of these telephone calls to be decided in line with PPI input and subject to parental preferences*).
- Once the child's ear pain has resolved and the parent has no further use for the trial medicine, the parent will be asked to return the ear drops bottle to the study team. Prepaid, addressed packaging will be provided to parents for this purpose. Adherence will be measured by weighing the liquid remaining in the ear drop bottles.
- The parent will also be asked to record the child's antibiotic consumption at each of the 8 time points within the Symptom and Recovery Questionnaire (Days 1-8), and to return the packaging of any antibiotics used to the study team at the same time as the used ear drops. Again, parents will be provided with specific prepaid return packaging for this.

In the event that the drops are effective, it is possible they will be used more frequently in the active than control arms and adherence data will allow a secondary 'per protocol' analysis.

7.7. Use of alternative rescue therapies i.e. oral analgesics

Our PPI group has confirmed that parents will wish to use rescue therapy in the event of ongoing pain. Responsible Clinicians will be asked to provide standardised advice regarding the stepped use of oral analgesics, starting with: (i) paracetamol; (ii) switching to ibuprofen;¹¹ and (iii) using both together or alternating.¹² If the drops provide effective analgesia then it is likely that oral analgesic use will be higher in the placebo group and this could reduce the observed effect of active drops on pain. We will measure use of rescue paracetamol, ibuprofen and other pain-killing therapies (through the Symptom and Recovery Questionnaire) and both adjust for any differences between groups in our multivariable model (if necessary), and investigate the relationship between the contemporaneous use of ear drops and other analgesics (including interactions) on outcomes.

7.8. Concomitant medication

See exclusion criteria (which are informed by the 'interactions' stated in the Australian Government Department of Health Therapeutic Goods Administration (TGA)-approved Product Information, Appendix 8).

At the discretion of the responsible clinician, and in line with NICE guidance, parents may be offered either no antibiotic, a delayed (rescue) antibiotic prescription or a same day antibiotic prescription (of the clinician's choice). For children recruited to the RCT or OCS, parents in receipt of a delayed antibiotic prescription will be advised to delay giving antibiotics to the child as per NICE guidelines. Children will continue medication for other acute and chronic conditions as advised by their GP as long as these are consistent with the eligibility criteria. Parents will be advised not to use other benzocaine-containing products while using the trial ear drops.

7.9. Known side effects

According to the SmPC equivalent provided by the manufacturer (received direct from Pfizer, Australia on 09 December 2015), which is the TGA-approved Product Information for Auralgan Ear Drops (PI-Auralgan_2015-05-07A, approved by TGA on 16 April 2014, and last updated on 03 July 2015; see Appendix 8), no known, expected side effects are associated with the use of Auralgan.

Furthermore, the known side effects associated with topical benzocaine or phenazone application reported in the Product Information are rare and considered to be "unlikely following application of Auralgan on the external ear canal".

A detailed review of the safety risks of Auralgan, specifically focusing on the risks of benzocaine-induced methaemoglobinaemia, has been conducted by the investigators (December 2015), including a review of benzocaine-associated reported adverse reactions in the United States, Australia and the UK, and no reported serious adverse reactions were identified in which Auralgan was the primary suspected causal agent. This review included a query of the Database of Adverse Events Notifications for Australia (where Auralgan has been used as an OTC medicine for at least 50 years) which includes adverse event reports between 01 January 1971 and 19 August 2015, and this found a total of 11 reports for Auralgan during the reporting period. Although neither the age of the patients or the severity of the adverse events were reported, none of the events described in these reports corresponded to our definition of a Serious Adverse Event.

All of the information provided within the 'contraindications', 'precautions', 'interaction with other medicines' and 'adverse reactions' sections of the Product Information, as well as any information identified within the review of Auralgan/benzocaine-induced methemoglobinemia as pertaining to the theoretical risks of topical benzocaine and phenazone use, has been incorporated into the trial eligibility, training and operationalisation.

For the above reasons no adverse reactions related to the IMP are expected in this trial.

All adverse events, including any new or worsening symptoms, will be monitored in line with the trial monitoring SOP, but will only be reported if meeting the definition of a Serious Adverse Event and as per the trial Research Safety Reporting SOP (see section 8, Pharmacovigilance, below). Any SAE deemed related to the IMP will be reported as a Suspected Unexpected Serious Adverse Reaction (SUSAR) per the trial Research Safety Reporting SOP, Directive 2001/20/EC and CT-3.

Based on previous clinical experience with Auralgan no adverse events are expected in this trial, however the trial investigators wish recruiting primary care clinicians to be aware of the theoretical safety risks associated with the use of topical benzocaine and phenazone, as stated within the 'Adverse reactions' section of the Product Information, as follows:

Symptoms / signs

- Difficulty breathing
- Pale, gray or blue coloured (bluish) skin

- Severe tiredness/weakness/fatigue/inability to do physical activity
- Confusion, light-headedness, severe dizziness or headache
- Nausea, vomiting
- Dark urine
- Yellowing of the skin and the whites of the eyes (jaundice)
- Heart murmur or increased heart rate
- Enlarged spleen; enlarged liver
- Rash; urticaria; Burning/stinging/redness/new pain in or around the ears; itching/swelling (especially swelling of the ear/eye/ face/neck/throat/mouth/tongue)
- Oedema; anaphylaxis
- Vertigo; nystagmus
- Sensitisation / irritation: erythema and pruritus which may progress to vesiculation and oozing

Diagnoses

- Dyspnoea
- Cyanosis
- Methaemoglobinaemia
- Phenazone-induced haemolytic anemia and agranulocytosis
- Benzocaine toxicity
- Penetration of the local anaesthetic into the inner ear
- Benzocaine hypersensitivity reaction
- Contact dermatitis due to frequent exposure to ester-type local anaesthetics
- Angioedema

A summary of the rare complications, and recommendations for the diagnosis and treatment of benzocaineinduced methaemoglobinaemia, will be provided to clinicians within the Trial Participation Card.

We will advise the parents/carers of participating children which adverse signs to watch for in the Parent Information Sheet (PIS), through the recruitment process (information to be provided by recruiting primary care staff to parents), in printed ear drops instructions that will be provided to parents of all participating children in the ear drops arms of the trial, and in the Trial Participation Card, which will also be given to the parents of all children receiving ear drops within the trial. With reference to a single adverse event reported in the DAEN (ref: 207569, reported on 03/05/2005), we will also advise parents to stop giving ear drops if they appear to be associated with an increase in pain.

Parents/carers will be made aware of the following:

- Auralgan may cause harm if swallowed.
- When used in small doses, no COMMON side effects have been reported with Auralgan.
- Patients are advised to tell their doctor in the event of:
 - any of these unlikely but serious side effects: burning/stinging/redness/new pain in or around the ears.
 - o any of these rare but very serious side effects: bluish skin, severe tiredness/weakness.
 - any of the following symptoms of a rare but serious allergic reaction: rash, itching/swelling (especially swelling of the ear/eye/ face/neck/throat/mouth/tongue, a condition known as angioedema), severe dizziness, trouble breathing.

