APPENDIX 8: Auralgan Product Information (PI-Auralgan_2015-05-07A)

Due to its low aqueous solubility, benzocaine is poorly absorbed and systemic toxicity is rare however, methemoglobinemia has been observed following topical application.

Indications

Auralgan ear Drops is for the effective relief of ear pain associated with otitis media.

Contraindications

Auralgan Ear Drops is contraindicated for use:

- in patients with perforated ear drums
- if discharge from the ear is present
- in patients with known hypersensitivity to any of the ingredients in the product or to similar substances

Precautions

Auralgan Ear Drops should be used with caution in patients with the following ear problems:

- Pain lasting more than 24 hours
- Fever, dizziness, stiff neck, ear discharge
- Hearing loss or ringing in the ears
- Inability to walk properly
- In patients who have had a discharge from ears, a recent ear infection or had a burst ear drum in the past.

Carcinogenesis, mutagenesis, impairment of fertility: Long-term animal studies have not been performed to evaluate the carcinogenic or mutagenic potential of Auralgan Ear Drops. The effect of Auralgan Ear Drops on human fertility is not known.

Auralgan Ear Drops should be used with caution in patients with porphyria as phenazone is possible porphyrogenic.

This product should be kept out of reach of children.

Due to a potential increased risk of methemoglobinemia, use with caution in the following patients:

- Patients taking drugs such as sulphonamides or antimalarials as these may predispose to methemoglobinemia.
- Infants under 1 year of age.
- Patients with hemoglobinopathies or Glucose-6-phosphate dehydrogenase deficiency (G6PD).

Stop use and seek immediate medical attention if you have difficulty breathing; pale, gray or blue colored skin; weakness, confusion, or headache. These may be signs of a rare, but serious condition and may appear within minutes to hours after benzocaine use.

PI- Auralgan_2015-05-07A

Use in pregnancy

The safe use of Auralgan Ear Drops during pregnancy has not been established.

Lactation

Available evidence and/or expert consensus is inconclusive or is inadequate for determining infant risk when used during breastfeeding. Therefore it is not recommended for breastfeeding mothers unless the potential benefits to the patient are weighed against the possible risk to the infant.

Interaction with other medicines

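### Section 7.9 has parents report possible methaemoglobinaemia signs to a doctor, where Appendix 8 says to stop the drops and get immediate care; confusion and headache are left off the parent list

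*Protocol*

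**What the plan says.** Section 7.9 gives clinicians one list of signs and parents another. The clinician list includes "Pale, gray or blue coloured (bluish) skin" and "Confusion, light-headedness, severe dizziness or headache", along with difficulty breathing and severe tiredness or weakness.

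The parent list is introduced by "Patients are advised to tell their doctor in the event of". Under it come burning, stinging, redness or new pain around the ear; "any of these rare but very serious side effects: bluish skin, severe tiredness/weakness"; and allergic signs ending in "severe dizziness, trouble breathing". The only instruction to stop in that text concerns pain: "we will also advise parents to stop giving ear drops if they appear to be associated with an increase in pain".

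Appendix 8, under Precautions, reads "Stop use and seek immediate medical attention if you have difficulty breathing; pale, gray or blue colored skin; weakness, confusion, or headache", and explains that the signs "may appear within minutes to hours after benzocaine use". Section 7.9 also states that everything in the product information's precautions and adverse-reactions sections has been carried into eligibility, training and operation of the trial.

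**The concern.** The parent advice in section 7.9 is weaker than the source it says it has incorporated. It gives a contact action with no urgency and no instruction to stop dosing, for signs that the product information treats as needing both. It also shortens the list of signs for parents, who see the child between doses.

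The sponsor plainly takes benzocaine-induced methaemoglobinaemia seriously. Section 6.1 sets the lower age limit at 12 months because of it, and the amendment history in Appendix 1 ties the dosing limits to benzocaine toxicity thresholds. If the parent materials follow section 7.9 as written, a parent who notices a warning sign could wait to reach a doctor and keep giving drops meanwhile, without departing from the protocol.

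**Working it through.** The check is mainly a comparison of text.

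**Signs.** Each of the five groups in Appendix 8 (Precautions) is set against the two lists in section 7.9.

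| Appendix 8 sign group | Parent list | Clinician list | Stop or urgent-care action for parents |
|---|---|---|---|
| Difficulty breathing | Named (among allergic signs) | Present | None |
| Pale, grey or blue skin | Partly: bluish only | Present | None |
| Weakness | Named, as severe tiredness or weakness | Present | None |
| Confusion | Absent | Present | None |
| Headache | Absent | Present | None |

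Parent list: 2 named + 1 partly covered + 2 omitted = 5. Clinician list: 5 of 5. Stop or urgent-care action in the parent text: 0 of 5.

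**Is the instruction given elsewhere?**
- Sections 9.10 and 9.17 tell parents to withhold or stop the drops, but for ear discharge. Section 7.9 does so for increased pain. The protocol therefore writes a stop instruction where it wants one.
- Section 7.4 allows dosing up to every 2 hours, 12 times a day, for at most 8 days, until pain is relieved. It names no stop for these signs.
- Section 9.7 gives parents a card with emergency numbers, to show to a clinician in an emergency. As described, it does not say which signs are an emergency or that dosing should stop.
- Section 9.17 places the support calls on Monday to Friday, so they cannot be relied on for a reaction that develops within hours.

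**A smaller mismatch.** Appendix 8 (Adverse reactions) calls for prompt discontinuation on sensitisation or irritation. Section 7.9 puts burning, stinging and redness under telling the doctor, and the stop advice for increased pain covers this only in part.

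**Illustration of delay.** Further doses allowed = hours until a doctor is reached ÷ 2 hours per dose (section 7.4). The waiting time is assumed, since the protocol gives none:
- 2 hours: 2 ÷ 2 = 1 dose
- 6 hours: 6 ÷ 2 = 3 doses
- 12 hours: 12 ÷ 2 = 6 doses

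These are upper bounds; the age-specific maximum in section 7.4 may reduce them. They show what the dosing rule permits and do not predict what parents would do.

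**The case against.** The strongest reply is that section 7.9 only summarises content. The working instructions are the Parent Information Sheet, the recruiting clinician's explanation, the printed drop instructions and the Trial Participation Card. None is shown, and any may be stronger. This stands as a limit on the consequence, but section 7.9 names those same channels as the carriers of its advice, so its wording still needs to be right.

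Section 7.9 also says the precautions have been incorporated, which can be read as a commitment to the missing instruction. The specific parent text a few paragraphs later does not honour it, so the general statement sharpens the inconsistency.

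Appendix 1 records that section 7.9 was revised on regulator advice, including the information for parents on rare side effects. That shows the wording was reviewed. It does not show that anyone endorsed advice weaker than the product information.

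Headache and mild weakness are common in febrile children, so copying Appendix 8 word for word could send many children to urgent care needlessly. This stands, and the fix allows for it. It does not explain the absence of confusion or of pale or grey skin, or the lack of a stop for any of the signs.

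The irritation point is the weaker part: the discontinuation advice in Appendix 8 follows a sentence about people frequently exposed to this class of anaesthetic, and it overlaps with the existing advice on pain. Few parents told that blue skin is very serious would go on dosing for 12 hours, so the dose illustration carries little weight. The finding does not depend on it.

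**Conclusion.** The concern holds. As written, the parent advice in section 7.9 is weaker than Appendix 8: no stop or urgent-care action for any of five sign groups, two groups omitted, and one covered only in part. No other section supplies the instruction.

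The text does call bluish skin and weakness very serious and does send the parent to a doctor, so the shortfall is in urgency and stopping. No event rate or number of affected children is claimed. Harm is expected to be rare: section 7.9 cites 11 Australian reports between 1971 and 2015, none matching the trial's definition of a serious adverse event, although severity was not reported. The practical consequence depends on the parent materials following section 7.9. No endpoint or analysis is wrong because of this. It should be fixed because the reaction is time-critical, the participants are children from 12 months of age, and the correction is small.

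**What to change.** Amend the parent advice in section 7.9 in two tiers.

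1. Stop the drops and seek immediate medical attention for difficulty breathing; pale, grey or blue skin; severe tiredness or weakness; confusion; or signs of a serious allergic reaction. The sponsor's clinicians should set the threshold for headache and milder weakness.
2. Stop the drops and contact the doctor for burning, stinging or redness in or around the ear.

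Then check the Parent Information Sheet, the printed drop instructions and the Trial Participation Card against the amended text, and change only those that fall short.

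The cost is one wording amendment to the ethics committee and the MHRA (section 14.3) and a check of three documents. No visits, staff or participants are added. If the card or the drop instructions need changing, sealed Patient Packs already made up (section 7.2) would have to be updated or replaced. A few more children, some on placebo, may stop early or be taken to urgent care, which would slightly lower adherence in both drop arms.
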